## [ON-LINE SURVEY - PROGRAMMER: RANDOMIZE THE ORDER OF THE FIRST 3 RESPONSE OPTIONS]

14. According to the Piqray Prescriber's/HCP Guide for Hyperglycemia and SmPC for Piqray, please indicate if the following statement is True or False: If Piqray dosing is interrupted due to elevations in fasting glucose >250 mg/dL (>13.9 mmol/L), and fasting glucose decreases to ≤160 mg/dL (≤8.9 mmol/L) within 3-5 days under appropriate antihyperglycemia treatment, Piqray can be resumed at the starting dose level of 300 mg/day. [KEY QUESTION]

D True

✓ False

□ I don't know/am not sure

- According to the Piqray Prescriber's/HCP Guide for Hyperglycemia and SmPC for Piqray, when hyperglycemia occurs and patients are treated with antihyperglycemic medication, at what frequency should fasting glucose continue to be monitored? [KEY QUESTION]
  - Daily for the first 4 weeks, then weekly for the next 8 weeks

 $\checkmark$  Weekly for at least 8 weeks, followed by once every 2 weeks, and consider consultation with a healthcare professional with expertise in the treatment of hyperglycemia.

As clinically indicated

I don't know/am not sure

[ON-LINE SURVEY - PROGRAMMER: RANDOMIZE THE ORDER OF THE FIRST 3 RESPONSE OPTIONS]

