#### 7.3.1 **Outcomes/endpoint variables**

Primary endpoint:

- Levels of knowledge of the risk for hyperglycemia, and risk factors for hyperglycemia, (survey question 4A, 6),
- Levels of knowledge of signs and symptoms of hyperglycemia (survey questions 5A-C), •
- Levels of knowledge of recommendations for monitoring for hyperglycemia prior to, and during, treatment with Pigray (survey questions 8A-C, 10, 15) and
- Levels of knowledge of recommendations for managing hyperglycemia during treatment ٠ with Piqray (survey questions 12-14).

The primary endpoint is a composite endpoint that combines correct responses given by HCPs to questions included in the composite. Specifically, the primary endpoint is a weighted composite knowledge score aggregated across the following survey questions: 4A, 5A-C, 6, 8A-C. 10, and 12-15. It is calculated as the number of all correctly answered questions divided by the number of all answered questions (i.e. questions that were answered either correct and not correct – unanswered questions are excluded).

Success criteria on the primary endpoint is defined as a weighted composite knowledge level of at least 70% across these key questions.

Secondary endpoint questions:

- Levels of reported receipt and reading of the Pigray Prescriber's/HCP Guide for • hyperglycemia, assessed as the percentages of HCPs who report receipt and reading of the same (survey questions 1, 2)
- HCPs' knowledge levels for each survey question regarding knowledge of, and • management of, hyperglycemia, assessed as the percentages of HCPs with correct responses to each question (individual responses to survey questions 4-15)
- The distribution of responses regarding the primary source from which HCPs learned • about the messages included in the Piqray Prescriber's/HCP Guide for Hyperglycemia, assessed as the percentages of HCPs who report using each of the possible sources as the primary source they used (survey question 3).

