#### [ON-LINE SURVEY - PROGRAMMER: RANDOMISE THE ORDER OF THE FIRST 4 RESPONSE OPTIONS]

7. According to the Piqray Prescriber's/HCP Guide for Hyperglycemia and SmPC for Piqray, please indicate if the following statement is True or False: For patients at higher risk for developing hyperglycemia, there is no need to consult with a healthcare professional or endocrinologist experienced in the treatment of hyperglycemia.

🗆 True

✓ False

□ I don't know/am not sure

8. According to the Piqray Prescriber's/HCP Guide for Hyperglycemia and SmPC for Piqray, to mitigate risk of hyperglycemia, which of the following should be performed before a patient starts treatment with Piqray?

|   |  | Check the box if
the action should
be performed |
|---|--|---|
| Α | Obtain a fasting glucose and
HbA1c  | 1   |
| В | Optimize the patient's level of
blood glucose, as applicable                      | 1   |
| с | Counsel the patient about the risk of hyperglycemia                                  | 1   |
| D | Increase the dose of their current
antihyperglycemic medication, if
applicable |   |
| E | Consult with a diabetologist for
all patients, even if they are not
diabetic   |   |
| F | I don't know/am not sure   |   |

[ON-LINE SURVEY - PROGRAMMER: RANDOMIZE THE ORDER OF THESE 5 QUESTIONS]  According to the Piqray Prescriber's/HCP Guide for Hyperglycemia and SmPC for Piqray, please indicate if the following statement is True or False: The monitoring schedule of fasting glucose levels for patients receiving Piqray is the same for patients with, and without, risk factors for hyperglycemia.

D True

✓ False

□ I don't know/am not sure

10. According to the Piqray Prescriber's/HCP Guide for Hyperglycemia and SmPC for Piqray, at what frequency should fasting glucose testing be performed for all patients treated with Piqray?

□ Weekly for the first 3 months of treatment, then monthly thereafter

✓ At weeks 1, 2, 4, 6, and 8 after treatment start, then monthly thereafter □ Daily for the first 2 weeks of treatment, then at Weeks 4, 6, and 8, then monthly thereafter

□ I don't know/am not sure

[ON-LINE SURVEY - PROGRAMMER: RANDOMIZE THE ORDER OF THE FIRST 3 RESPONSE OPTIONS]

11. According to the Piqray Prescriber's/HCP Guide for Hyperglycemia and SmPC for Piqray, at what frequency should HbA1c testing be performed for all patients treated with Piqray?

Monthly for the first 3 months of treatment, then quarterly thereafter

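### Key question 15 asks only for a monitoring frequency, but its keyed option is twice as long as the next and alone carries a consultation clause, so it may credit respondents who do not know the schedule

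*Protocol*

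**What the plan says.** The stem of question 15 (Protocol, Appendix 13.1) concerns patients in whom hyperglycemia has occurred and who are receiving antihyperglycemic medication. It asks "at what frequency should fasting glucose continue to be monitored? [KEY QUESTION", the last words being the marker for a primary-endpoint item. The response options are:

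- "Daily for the first 4 weeks, then weekly for the next 8 weeks"
- the ticked option, "Weekly for at least 8 weeks, followed by once every 2 weeks, and consider consultation with a healthcare professional with expertise in the treatment", which ends by naming hyperglycemia
- "As clinically indicated"
- "I don't know/am not sure"

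Table 7-1 describes the variable as knowledge of the monitoring frequency, yet counts the whole compound option, consultation included, as the correct answer.

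Section 7.3.1 defines the primary endpoint as a score "aggregated across the following survey questions: 4A, 5A-C, 6, 8A-C. 10, and 12-15", calculated as "the number of all correctly answered questions divided by the number of all answered questions". Success is a composite of at least 70%, and section 7.7.2 compares the point estimate with that threshold. Section 7.3.1 also makes the percentage correct on each of questions 4-15 a secondary endpoint, so question 15 is reported on its own as well.

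Section 7.6 gives the safeguards for multiple-choice items: randomised response sets, completion in one sitting, and no revision after moving on. Appendix 13.1 mentions a pre-testing version of the questionnaire but gives no criterion for judging items.

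**The concern.** An item measures knowledge of a schedule only if someone without that knowledge cannot pick out the right option from its form. Here the keyed option stands out twice. It is much the longest, and it adds advice to consider expert help, which the stem did not ask for and which reads as prudent. A respondent unsure of the schedule, but confident that seeking advice is sensible, can tick it and be scored as knowing the schedule.

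Respondents who know the schedule would mostly choose that option anyway, so the cue acts chiefly on those who do not. The expected direction is therefore upward, towards the success threshold. A larger sample does not reduce such a bias, and the confidence interval does not show it. Randomising the order moves the option around the screen but leaves its length and content as they are.

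**Working it through.** **1. Option lengths (counted from Appendix 13.1).**

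| Item | Keyed option, words | Other substantive options, words |
|---|---|---|
| Question 15 | 26 | 13 and 3 |
| Question 15, frequency part only | 12 | 13 and 3 |
| Question 10 | 14 | 11 and 18 |
| Question 11 | 10 | 11 and 11 |

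The ratio for question 15 is 26/13 = 2.0 in words and 167/61 = 2.7 in characters. The consultation clause accounts for 26 - 12 = 14 words. Without it the keyed option is slightly shorter than the longest distractor, so the whole length cue comes from the clause. The other two frequency items, questions 10 and 11, do not have the fault.

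**2. Weight in the composite.** The list in section 7.3.1 is 4A, 5A, 5B, 5C, 6, 8A, 8B, 8C, 10, 12, 13, 14 and 15, which is 13 items. If all are answered, question 15 carries 1/13 = 7.7%. Table 7-1 and the questionnaire also mark 5F-H as key questions. With those there would be 16 items and a weight of 1/16 = 6.25%.

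**3. The plan's precision, for scale.** Table 7-4 gives exact 95% intervals at 70% knowledge of 50.6-85.3 (n = 30) and 55.4-82.1 (n = 50). Recalculated Clopper-Pearson limits agree. The half-widths are (85.3 - 50.6)/2 = 17.35 and (82.1 - 55.4)/2 = 13.35, matching the stated 17.4 and 13.4.

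**4. Possible size.** Let u be the share who do not know the schedule, d the share of those who tick the don't-know option, and g the chance that a guesser picks the keyed option once cued. With three substantive options the uncued chance is 1/3.

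- Item gain = u x (1 - d) x (g - 1/3)
- Composite gain = item gain / 13

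The values of u, d and g are assumptions; the documents give none of them. Don't-know answers are counted as answered and not correct, in line with the item denominators in section 7.7.1.

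| u | d | g | Item gain (points) | Composite gain (points) |
|---|---|---|---|---|
| 30% | 0 | 60% | 0.30 x 0.267 = 8.0 | 0.6 |
| 40% | 0 | 60% | 0.40 x 0.267 = 10.7 | 0.8 |
| 40% | 0 | 80% | 0.40 x 0.467 = 18.7 | 1.4 |
| 50% | 0 | 80% | 0.50 x 0.467 = 23.3 | 1.8 |
| 40% | 50% | 60% | 0.20 x 0.267 = 5.3 | 0.4 |
| 40% | 50% | 80% | 0.20 x 0.467 = 9.3 | 0.7 |

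With 16 items the composite gains shrink by the factor 13/16; the largest becomes 23.3/16 = 1.5 points.

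**The case against.** The strongest reply is that nothing here has been observed. There are no response or pre-test data, the share not knowing and the cued hit rate are assumed, and the don't-know option gives an unsure respondent somewhere else to go. The cue may also be weaker than it looks. Daily monitoring at the start could strike some respondents as the more careful choice, clinical discretion is a plausible answer for a practising prescriber, and the added clause might put off someone who knows the schedule but doubts the rest. All of this stands as a limit on size and certainty. A reader might infer that question 15 is inflated as a matter of fact; the documents support only that it is liable to be.

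A second reply is that the wording looks deliberate. Table 7-1 repeats the compound answer, and the stem refers to the Guide and SmPC, which are not at hand. That is a reason to keep the consultation message somewhere in the survey. It does not justify attaching it to one option of a question about frequency.

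A reader might also infer that the clause can simply be deleted because question 7 already tests consultation. It does not test the same thing. Question 7 asks whether, for patients at higher risk of developing hyperglycemia, "there is no need to consult with a healthcare professional or endocrinologist experienced in the treatment of hyperglycemia". Question 15 concerns patients in whom it has already occurred, and question 7 is not in the composite.

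Finally, pre-testing is foreseen and could catch the problem, but the protocol sets no criterion that would make it do so.

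**Conclusion.** The point holds as a minor item-writing fault. The keyed option of a primary-endpoint question is marked out by its length and by a clause that does not answer the stem, and no stated safeguard removes the cue. The likely direction is upward.

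On the assumptions shown, the composite gain is between about 0.4 and 1.8 points. That is small beside the stated precision of 13.4-17.4%. It could change the conclusion only where the composite without the cue fell just short of the threshold, at most between 70 - 1.8 = 68.2% and 70%. The documents do not support a stronger reading, that this item could carry an otherwise clearly failing survey past 70%: its entire weight is 7.7%.

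The effect is undiluted in the item-level secondary endpoint, where question 15 could read about 5 to 23 points too high on the same assumptions.

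**What to change.** Before the questionnaire is programmed and translated, make the substantive options of question 15 parallel in one of two ways:

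- **Limit every option to a frequency** (13, 12 and 3 words) and move the consultation message to a separate short item outside the composite, worded for patients in whom hyperglycemia has occurred. The composite stays at 13 items and the message is still tested.
- **Attach the same consultation clause to every substantive option** (27, 26 and 17 words). This needs no new item, but the consultation message is then shown rather than tested.

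Under either route, align the question 15 row of Table 7-1, and do not rely on question 7 to cover the message. The monitoring schedule and the clinical content stay as they are.

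The cost is one wording edit and possibly one extra short item with its Table 7-1 row and translations. After launch the same edit would split respondents across two versions of a primary-endpoint item, so it is worth making only beforehand. Priority is low: a cheap improvement, not a condition for proceeding.

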#### PARTICIPANT CHARACTERISTICS

[Preamble 2]: There are just a few more questions to help us combine your answers with other answers we have received, and to help us interpret the survey results.

- 16. What is your primary medical specialty? (Please tick 1 response only)
  - □ Surgeon/surgical oncologist
  - □ Radiation oncologist/radiologist
  - Medical oncologist
  - □ Other

| Novartis
Non-Interve | entional Study Protocol v00  | Confidential | Page 41
BYL719/alpelisib/CBYL719C2005 |
|-------------------------|--|--------------|--|
|                         |  |              |  |
| 17.                     | Approximately how a  |              |  |
|                         | 
 
□ <5 years
 
□ 5 to <10 years
 
□ 10 to <15 years
 
□ ≥15 years
 
□ Prefer not to answe
 
 |              |  |
| 18.                     | Within the past 12 m
Piqray?  |              |  |
|                         | □ 1-5
□ 6-10
□ >10
□ I don't know/am no   |              |  |
| 19.                     | When was the last tin  |              |  |
|                         | □ <3 months ago
□ 3 to <6 months ago
□ I don't know/am no  |              |  |
| 20.                     | Have you been an inv   |              |  |
|                         | □ Yes
□ No
□ I don't know/am no  |              |  |
| CLO                     | SING   |              |  |
| Than                    | k you for taking the ti  |              |  |
| Your                    | may now close this brow  |              |  |
